## 9.0 Vulnerable Populations

Vulnerable Populations:

Population / Group	Identify whether any of the following populations will be targeted, included (not necessarily targeted) or excluded from participation in the study.
Children	Excluded from Participation
Pregnant women/fetuses/neonates	Excluded from Participation
Prisoners	Excluded from Participation
Adults lacking capacity to consent and/or adults with diminished capacity to consent, including, but not limited to, those with acute medical conditions, psychiatric disorders, neurologic disorders, developmental disorders, and behavioral disorders	Excluded from Participation

MEDICAL PROTOCOL (HRP-590)

PROTOCOL TITLE: Brivaracetam to Reduce Neuropathic Pain in Chronic SCI: A Randomized, Double-Blind, Placebo-Controlled Clinical Trial

VERSION DATE: v7.0 APR2024

Non-English speakers	Included/Allowed to Participate
Those unable to read (illiterate)	Included/Allowed to Participate
Employees of the researcher	Excluded from Participation
Students of the researcher	Excluded from Participation
Undervalued or disenfranchised social group	Included/Allowed to Participate
Active members of the military (service members), DoD personnel (including civilian employees)	Included/Allowed to Participate
Individual or group that is approached for participation in research during a stressful situation such as emergency room setting, childbirth (labor), etc.	Excluded from Participation
Individual or group that is disadvantaged in the distribution of social goods and services such as income, housing, or healthcare.	Included/Allowed to Participate
Individual or group with a serious health condition for which there are no satisfactory standard treatments.	Targeted Population
Individual or group with a fear of negative consequences for not participating in the research (e.g. institutionalization, deportation, disclosure of stigmatizing behavior).	Excluded from Participation
Any other circumstance/dynamic that could increase vulnerability to coercion or exploitation that might influence consent to research or decision to continue in research.	Excluded from Participation

Additional Safeguards:

This project aims to research an intervention that may help vulnerable adults with spinal cord injuries reduce severe neuropathic pain, a severe health condition. To provide additional safeguards to protect individuals that may be vulnerable we:

- Will provide assurance of confidentiality, freedom to decline to participate, right to withdraw at any time without penalty.
- Engaged the SCI community in the planning of this research.
- We have assessed the permissibility of the physician-investigator to obtain consent for research.
- We will emphasize the risks and demands of this study participation to potential participants.
- We will provide short forms and a translator to individuals who are unable to read or speak in English.
- Groups included in the research where participant status in the group might be unknown (incidental enrollment), as group status is not solicited by the research team (ex: military status, if study teams don't ask and it doesn't impact the research):

The vulnerable population groups that are allowed to participate will not be identified and information will not be collected as to a patient's vulnerable population status. This research does not add risk to this group.

## **10.0 Local Number of Participants**

Local Number of Participants to be Consented:

We expect to screen 200 individuals to enroll 48 participants. We expect 20% attrition, therefore we anticipate a total of 40 participants will complete the study.

We anticipate enrolling a minimum of 12 participants and up to a maximum of 48 participants.

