## **5.0 Procedures Involved**

**Study Design:**

This is a randomized, double-blind, placebo-controlled clinical trial in 40 adults at least 18 years of age with SCI. Participants who meet the eligibility criteria (described in Section 8.1) will be randomly assigned with a 1:1 ratio to active drug (escalating brivaracetam dose to 100 mg twice daily for four weeks) or placebo using a randomization schedule developed by our biostatistician. This is a simple computer generated 1:1 scheme that randomly assigns participants to arm C or arm D. Study participants, research coordinators, and study personnel involved in outcomes assessments and analyses will all be masked to allocation. The drug will be provided by RxArtisans pharmacy in Wayzata, MN. The active and placebo capsules will have identical appearance and consistency. Treatment assignment will be known only to the investigational drug pharmacy (RxArtisans). We will register this trial at [www.clinicaltrials.gov](http://www.clinicaltrials.gov).

Study Procedures:

Overview of study procedures/study interventions. This study involves research activities that occur in-person, over the phone, and via online REDCap surveys. Participants will also have the option to participate entirely remotely. In this circumstance, there will be no MRI scan nor blood draw for banking; instead, all required safety labs will be completed with the participant's primary care physician and insurance will be charged and the participant will be responsible for any associated copays or costs. All research activities are summarized in Table 1 below and described in detail in the subsequent text.

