### 15.2 Power Analysis:

We present power and sample size analysis for the primary endpoint; a 2-point improvement in neuropathic pain intensity as assessed by the

International Spinal Cord Injury Pain Basic Dataset. We based our sample size calculation on variations in pain intensity observed in an ongoing clinical trial (DoD W81XWH-14-SCIRP-CTA, [name] PI). In this sample, average neuropathic pain intensity in 28 adults with SCI was  $3.43 \pm 3.17$ . Based on this, a sample size of 20 per arm will have more than 80% power to detect a significant difference in pre-post changes of neurological pain between the two arms at a two-sided significance  $\alpha$  level of 0.05. This sample size is sufficient to address the exploratory analyses proposed in Aims 2-3.

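### Section 10.0 gives 40 completers from 48 enrolled at 20% attrition; its own figures give about 38, and the sample-size targets in Sections 5.0, 10.0 and 15.2 do not agree

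*Combined protocol and SAP*

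**What the plan says.** Three places in the protocol bear on trial size.

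- **Section 10.0, Local Number of Participants.** "We expect to screen 200 individuals to enroll 48 participants". The next sentence reads "We expect 20% attrition, therefore we anticipate a total of 40 participants will complete the study". The section then gives a range: "We anticipate enrolling a minimum of 12 participants and up to a maximum of 48 participants". So 48 is both the expected enrolment and the upper limit.
- **Section 5.0, Study Design.** "This is a randomized, double-blind, placebo-controlled clinical trial in 40 adults at least 18 years of age with SCI".
- **Section 15.2, Power Analysis.** The claim is that "a sample size of 20 per arm will have more than 80% power" for a 2-point difference at a two-sided 5% level. The text does not say whether the 20 are randomised, completing or analysed.

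Three further statements affect how these numbers should be read. Section 15.1 makes intention-to-treat the main analysis and gives no method for missing outcomes. Footnote c to Table 1 schedules the Visit 3 assessments at early withdrawal for participants who do not complete. The termination procedures in Section 12.0 keep data already collected in the analysis unless the participant asks for it to be withdrawn.

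**The concern.** The sentence in Section 10.0 presents 40 as the result of applying 20% attrition to 48, and it is not. The 48 looks like the common inflation slip of multiplying the target by 1 plus the attrition rate instead of dividing by 1 minus it. Because 48 is also the maximum, the enrolment plan has no room to absorb the difference.

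The second difficulty is that 40 appears as the size of the trial in Section 5.0 and as the number completing in Section 10.0. Twenty per arm in Section 15.2 fits either. If 40 were the number randomised, the plan's attrition rate would leave far fewer than 40 with complete follow-up. A reader cannot tell which number recruitment has to reach, or which one the power statement depends on.

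**Working it through.** **Inputs.** Enrolment 48, attrition 20%, stated completers 40 (Section 10.0). Trial of 40 adults (Section 5.0). Twenty per arm, difference 2 points, SD 3.17, two-sided 0.05 (Section 15.2).

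**1. The plan's own figure.** Completers = enrolled x (1 - attrition) = 48 x 0.80 = 38.4, about 38, or 19 per arm if balanced. The stated 40 is 1.6 participants higher, about 4%.

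**2. Where 48 may come from.**
- 40 x (1 + 0.20) = 48, which matches the plan exactly.
- 40 / (1 - 0.20) = 50, the enrolment that 40 completers would need at 20% attrition.
- 1 - 40/48 = 16.7%, the attrition at which 48 enrolled would leave 40.

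**3. How far off the expectation is.** Assume that each of 48 participants completes independently with probability 0.80. The chance of at least 40 completers is then 36%. So 40 is possible, but it is not the expected number.

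**4. The 40 in Section 5.0.** If 40 were the number randomised, 40 x 0.80 = 32 would complete, 16 per arm if balanced.

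**5. Effect on power.** Two-sample t-test, noncentrality = difference / (SD x sqrt(1/n1 + 1/n2)), two-sided 0.05. The plan gives an SD of pain intensity but neither an SD of change nor a pre-post correlation, so two values are shown. The first is 3.17, used as it stands. The second is 2.20, an assumption: the SD of change that gives exactly 80% at 20 per arm.

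| Per arm | Noncentrality, SD 3.17 | Power, SD 3.17 | Noncentrality, SD 2.20 (assumed) | Power, SD 2.20 (assumed) |
|---|---|---|---|---|
| 20 and 20 | 2/(3.17 x sqrt(2/20)) = 1.995 | 49.4% | 2/(2.20 x sqrt(2/20)) = 2.875 | 80.0% |
| 19 and 19 | 2/(3.17 x sqrt(2/19)) = 1.945 | 47.3% | 2/(2.20 x sqrt(2/19)) = 2.802 | 77.8% |

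The loss from 20 to 19 per arm is 49.4 - 47.3 = 2.1 points, or 80.0 - 77.8 = 2.2 points. It is about 2 points on either SD.

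**The case against.** The strongest reply is that the slip changes little. Section 15.2 does not call its 20 per arm completers. The main analysis is intention-to-treat, withdrawals are scheduled for the Visit 3 assessments, and their data are kept. With 48 randomised the expected number is 24 per arm, so the number analysed could exceed 20 per arm even though fewer than 40 complete. This stands, and it limits the consequence. It does not rescue the sentence in Section 10.0, which is about completers, or the conflict with 40 adults. Nor does it settle how many will contribute an outcome, because no missing-data method is given and some withdrawals may not be assessed.

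Stronger readings are tempting, and the documents do not support them:

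- **That the design can deliver no more than about 19 per arm.** This equates completing with being analysed. Even for completers, 38 is an expectation and not a ceiling.
- **That the allocation must be changed to blocks.** Section 5.0 says "This is a simple computer generated 1:1 scheme that randomly assigns participants to arm C or arm D" and mentions no blocking. Simple randomisation does not guarantee equal arms, but it is valid, and the planned unequal-variance t-test, rank-sum test and robust-error regression do not need them. At SD 3.17, a 28/20 split of 48 gives 56.0% power against 57.1% at 24/24, about 1 point. Blocking would be a design preference.
- **That the trial might be analysed with 12 participants.** The 12 is the lower end of an anticipated enrolment range. Nothing makes it an analysis or stopping size.
- **That the 49% in the table results from the attrition slip.** It results from using SD 3.17 at 20 per arm. The gap between that figure and the claimed power of more than 80% is a separate question.

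**Conclusion.** Section 10.0 is wrong as written. On its own figures 48 enrolled gives about 38 completers, while 40 completers needs either 50 enrolled or 16.7% attrition. The trial size in Section 5.0 conflicts with Section 10.0, and Section 15.2 leaves the meaning of its 20 per arm open.

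The consequence is small: about 2 percentage points of power at 19 against 20 per arm. That figure assumes balanced arms, a two-sample t-test, and 20 per arm meaning participants with complete follow-up. If withdrawals are assessed as Table 1 intends, the loss may be smaller or absent. The completer arithmetic needs none of these assumptions. This is a correction of stated figures and does not show that the design fails.

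**What to change.** 1. **Section 10.0:** state 48 enrolled, 20% attrition and about 38 completers. If 40 completers is to be kept with 48 enrolled, state 17% attrition instead and say why that rate is expected.
2. **Sections 5.0, 10.0 and 15.2:** give one target for participants randomised and one for participants completing, and use the same two numbers in all three places.
3. **Section 15.2:** say whether 20 per arm means randomised or completing. If it means completing, restate the power at 19 per arm.

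The cost is a text amendment with its usual review, plus one rerun of the power calculation if item 3 requires it. No extra participants are needed, and the randomisation schedule does not change.

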## **11.0 Local Recruitment Methods**

Recruitment Process:

The UMN healthcare system treats hundreds of patients with SCI each year. Given the large pool available for recruitment, we anticipate no difficulty in recruiting sufficient numbers of persons with SCI who meet the inclusion/exclusion criteria. Recruitment material will accurately reflect the study and will not be coercive.

*For self-referrals from recruitment materials:*

Participants may self-refer if they become aware of the study through recruitment materials, clinicaltrials.gov (or similar websites), or word of mouth referrals. A study-specific webpage will be published. A link to a REDCap online survey will be shared for individuals to indicate their interest and preferred contact method. Participants will self-enter their contact information prior to consent for contact purposes only.

Potential participants will be identified by Co-Investigators from patients under their care and their colleagues. Potential participants will be asked about their interest in the study at the time of a routine care visit. If interested, the patient will be given the choice to be approached by the investigator in person, over phone, or via e-mail, or have reach out to the investigator themselves. A flyer or recruitment card about the study may be sent to potential participants, asking them to contact study staff if they are interested.

Individuals who respond to the recruitment materials will complete a phone screen with study staff. If following the phone screen, the potential participant is eligible and interested, they will be required to seek medical clearance from their primary care physician, including a screening blood draw, one month prior to study Visit 1.

*Regional Healthcare Institutions:*

Contacts at regional healthcare institutions that have partnered with the University of Minnesota in previous SCI research will be made aware of this research, including the VA. Flyers and/or postcards/recruitment cards will be posted around campus, at the VA, on the UMN website (e.g., Brain Body Mind Lab website) and on social media with information about this study.

*Patient Representative Organizations (PRO):*

Recruitment information about this study will be provided to PRO's that will include sample text and flyers so they may distribute information about this study to their participating community members living with SCI. PRO's commonly use social media, newsletters, and share information at peer support groups to distribute information about the clinical trial. Targeted PRO's will include but will not be limited to Get Up Stand Up to Cure Paralysis, Minnesota Spinal Cord Injury Association, and Morton Cure Paralysis.

*University of Minnesota Spinal Cord Injury Research Recruitment Registry:*

We will utilize the Spinal Cord Injury Research Recruitment Registry managed by the UMN Department of Rehabilitation Medicine to help

facilitate enrollment. We will filter individuals in the registry based on inclusion/exclusion criteria and contact them via email or phone about this research opportunity.

*Online Clinical Trial Registries:*

This clinical trial will be listed on [www.clinicaltrials.gov](http://www.clinicaltrials.gov), [www.scitrials.org](http://www.scitrials.org), and other similar websites that assist community members to find and contact information about clinical trials.

*Local Community Presentations:*

The study team may hold presentations (digital or in-person) about this research and other projects and research results which may inform community members about this clinical trial which may result in recruitment.

*Social Media:*

Digital media may be shared on different social media platforms to notify potential participants about the clinical trial and how to contact the study team.

*Fairview Recruitment Mailing and MyChart Messaging:*

We will work with Fairview Research Services to identify individuals with SCI in the system and send recruitment mailings through the mail and/or MyChart messages, pending approval from the Fairview Research Administration. Patients who have opted out of having their records used for research will not be included.

*Identification of Potential Participants:*

Participants will be identified from the clinical partnerships listed in section 11.1. Study PI and physicians from our clinical partnerships will identify potential participants from their patient pools. These physicians have access to potential study participants' medical records and knowledge of their health history. Study staff will conduct prescreening over the phone or in-person to confirm eligibility at each site.

*Approaching potential participants in clinic:*

Potential participants will be identified by the Co-Investigator ([name]) and her team from among patients under her team's care and that of their colleagues who have legitimate access to their medical records. Through BPIC involvement, EPIC will be searched on the hits provided by BPIC. If eligible, a mailing will be sent out.

*Participants self-referred from recruitment materials:*

Potential participants will self-identify in response to flyer announcements via professional associations or support groups/word to mouth or other means.

We will use following approaches to identify participants through self-referrals:

- Postings on StudyFinder, a website managed by the UMN CTSI's Recruitment Center
- Postings on clinicaltrials.gov
- Identification via UMN's Research Match, an electronic volunteer recruitment registry
- Postings, flyers, or recruitment cards at the University of Minnesota and local rehabilitation centers; relevant websites and on professional social media sites (e.g., Facebook, Twitter).

Recruitment Materials:

The following recruitment materials will be used in this study: flyers or recruitment cards.

Payment:

Participants will receive up to \$350 for their time, effort, and to assist with transportation. Participants will receive \$150 after baseline testing (Visit 2), \$150 after end of study testing (Visit 3), and \$50 after Visit 4.

## **12.0 Withdrawal of Participants**

Withdrawal Circumstances:

At any time after enrollment, a participant may be discontinued. Reasons for discontinuation of a participant from the study will include, but may not be limited to, the following:

- The participant is found to be intolerant to a required study procedure at any time point
- Failure of the participant to adhere to protocol requirements
- Positive hGC for individuals of childbearing potential
- The participant experiences a serious adverse experience at any time point
- The participant develops an inter-current illness that would, in the judgment of the investigator, affect assessments of clinical status to a significant degree.
- The participant enrolls in another investigational study
- The participant requests to withdraw from the study

**Withdrawal Procedures:**

The PI and study physician will work closely with any participant wishing to withdraw from the study to ensure that the study drug is tapered appropriately and safely.

**Termination Procedures:**

Participation may be terminated due to drug intolerance or allergy and based on clinical judgement of the study team. All data collected will be retained and analyzed unless the participant specifically requests to have their data withdrawn from the analysis.

### **13.0 Risks to Participants**

**Foreseeable Risks:**

There is a risk of drug intolerance including allergy, suicidal behavior and ideation, somnolence and fatigue, psychotic symptoms, irritability, depression, loss of coordination/balance, constipation, aggressive behavior, and anxiety. All participants and caregivers will be educated to notify the PI or a health care provider if mood changes or suicidal behavior is observed. There is the risk of lowered seizure threshold for rapid drug withdrawal without tapering. There is some discomfort with venipuncture and there is the possibility of swelling and bruising at the site. There is also a slight chance that individuals become dizzy or faint. There are potential risks of loss of privacy and confidentiality. All participants will be encouraged to contact study staff, or an investigator regarding any side effects or adverse events that occur.

**MRI**

MRI machines use a strong magnet and radiofrequency magnetic fields to take images of your body. The scanning process is similar to an x-ray or CT scan, but MRI does not use ionizing radiation (high-energy radiation that can potentially cause damage to DNA) like x-rays or CT scans. The risks associated with MRI scans are:

- **Projectiles:** Objects with magnetic properties can be pulled into the magnet and turn into projectiles. To minimize this risk, we ask that participants remove all metallic items (watches, cell phones, hair pins, etc.) prior to entering the scanner and by controlling access to the scanner.
- **Claustrophobia:** The scanner is a long narrow tube that may cause some people to feel claustrophobic.
- **Hearing Damage:** The noise generated by the operation of the scanner during a study is loud enough to cause hearing damage

- if hearing protection is not worn. Hearing protection is required and is provided by the investigator.
- Nerve Stimulation: Some people experience localized tingling, twitching, or muscle contractions during MRI scans. We ask the participants to notify the investigator if this sensation is uncomfortable.
  - Disruption of Devices: Some devices can be damaged by magnetic fields and should not be brought into the scanner room. This includes some implanted devices such as pacemakers, cochlear implants, insulin pumps, nerve stimulators, etc. If participants have any implanted device, they are asked to notify the investigator.
  - Heating of Devices: The radiofrequency waves used in MRI can heat conductive materials. "The research team will utilize the CMRR Center's screening tools and adhere to the screening SOP during enrollment of all research participants in this protocol. The CMRR Center's screening tools and SOP are IRB approved under the CMRR Center Grant (HSC# 1406M51205) and information regarding screening procedures is publicly available on the CMRR website (CMRR Policies / Procedures).

### **Venipuncture**

There is some discomfort with venipuncture and there is the possibility of swelling, inflammation, and bruising at the site, and, in rare cases, the risk of infection. There is also a slight chance that individuals become dizzy or faint. All blood draws completed at the study site will be performed by a trained technician following standard clinical protocols to minimize risks.

